7.11.6 End of Efficacy Emergent Period

For all subjects, the end of Efficacy Emergent Period is defined as the treatment period up to the EOT Visit. Only exception for subjects who discontinued due to death, the last Hb assessment is taken as per convention the date of death is the EOT visit.

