6 ANALYSIS VARIABLES

6.1 Efficacy Endpoints

The **Efficacy Emergent Period** will be defined as the evaluation period from the Analysis date of first dose intake up to EOT Visit. This period will be used as reference period for the time to event analyses related to efficacy endpoints, unless specified otherwise. More details on the derivation of the date of End of Efficacy Emergent Period are provided in Section [7.11.6](#)

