In case that several Hb values are on the same day the average of these values will be used to represent the Hb of that day in the above formula. This calculation will provide the day that the change in Hb value occurs. The number of days that the Hb value has been in each category will be determined and the percentage calculated based on the length of time between the first and last Hb assessment during the evaluated period, i.e.:

Date of Last Hb assessment during the evaluated period – Date of first assessment during the evaluated period.

No imputation will be performed if no Hb value is available in relevant time windows.

In case a subject requires rescue therapy within 6 weeks prior to and during these 8-week evaluation periods, refer to Section 7.11.1 for imputation rules.

Potential Excessive Hematopoiesis (EH), regardless use of rescue therapy, based on Hb central laboratory

The presence of potential EH will be defined as:

- Hb increase by >2.0 g/dL between any 2 visits within 4 weeks of treatment

Time to first occurrence of potential EH regardless the use of rescue therapy during the treatment period will be defined in weeks as:

$$(\text{First event date} - \text{Analysis date of first dose} + 1) / 7$$

where ‘First event date’ is defined as first date of occurrence of the criterion met during the treatment period.

For a subject without potential EH, the time to censoring will be calculated (in weeks) as:

$(\text{Min}(\text{Date of last hemoglobin assessment during the Efficacy Emergent Period, End Date of the Efficacy Emergent Period}) - \text{Analysis date of first dose} + 1) / 7$

Refer to Section [7.11.6](#) for the definition of the Efficacy Emergent Period.

6.1.3.6 Occurrence (number) of hospitalizations, number of days of hospitalization per year and time to first hospitalization.

The occurrence and the number of non-HD hospitalizations per subject during the Efficacy Emergent Period will be calculated. HD days are not counted as hospitalizations, even when performed overnight.

The number of days of hospitalization per year treated will be calculated as:

$[\text{Sum of the durations of all non-HD hospitalizations in days (Date of discharge} - \text{Date of admission} + 1)] / (\text{duration of efficacy emergent period in days} / 365.25)$.

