In case of missing dates, the hospitalization duration will be imputed by the average duration per stay derived from the subjects with non-missing duration within the same treatment group. Duration of treatment exposure is defined in Section [6.5.4](#)

If the date of admission of a hospitalization record is the same as the date of discharge of the previous record, for example because two records are created to illustrate that the subject is moved from one hospital to another hospital or from a standard care to the intensive care unit (ICU), then the two records will be combined in one record.

Hospitalizations will also be described by reason for admission (admission for anemia or other reasons).

Time to first hospitalization in years will be defined in years as:

$(\text{First event date during the Efficacy Emergent Period} - \text{Analysis date of First dose intake} + 1) / 365.25$

With 'First event date' defined as 'Date of first Admission and 'Analysis Date of first dose intake' defined in Section [6.5.4](#)

For a subject without hospitalization, the time to censoring will be calculated as:

$(\text{Date of End of Efficacy Emergent Period} - \text{Analysis Date of first dose intake} + 1) / 365.25$

With date of End of Efficacy Emergent Period defined in Section [7.11.6](#)

6.1.3.7 Occurrence and time to first use of rescue therapy, occurrence and time to first use of RBC transfusions, number of RBC packs per subject, volume of RBC transfused per subject during the treatment period.

Rescue therapy is defined as RBC transfusion for all subjects and ESA (SC or IV) for roxadustat-treated subjects.

RBC transfusion is collected and coded into the ATC and WHO-DRL dictionaries. The following WHO-DRL codes will be classified as RBC transfusion: '01186901001'. ESA rescue treatment is recorded on the dosing CRF.

Only rescue medication that started during the study treatment and up to end of efficacy emergent period will be taken into account and considered as use of rescue medication.

For a subject with use of rescue therapy, the time to first use of rescue therapy will be calculated (in years) as:

$$(\text{First event date} - \text{Analysis Date of first dose intake} + 1) / 365.25$$

With 'First event date' defined as 'Date of first dose of rescue medication' during the Efficacy Emergent Period and 'Analysis date of first dose intake' defined in Section 6.5.4

For a subject without use of rescue therapy, the Time to censoring is calculated as:

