$$(\text{Date of End of Efficacy Emergent Period} - \text{Analysis date of first dose intake} + 1) / 365.25$$

With Date of End of Efficacy Emergent Period defined in Section 7.11.6

The volume of blood transfused and the total number of RBC units/packs (for each subject, the sum of blood volume and units/packs transfused) during the Efficacy Emergent Period will be calculated.

For RBC transfusions, when the number of units is not given but the volume transfused is given, the number of units will be estimated by volume transfused/250 mL (for transfusion of packed cell units) or volume transfused/500 mL (for transfusion of full blood).

For subjects with use of RBC transfusion, the time to first use of RBC transfusion is calculated as:

$$(\text{First event date} - \text{Analysis date of first dose intake} + 1) / 365.25$$

With 'First event date' defined as 'Date of first RBC transfusion' during the Efficacy Emergent Period and 'Analysis Date of first dose intake' is defined in Section 6.5.4

For a subject without use of RBC transfusion, the Time to censoring is calculated as:

$$(\text{Date of End of Efficacy Emergent Period} - \text{Analysis date of first dose intake} + 1) / 365.25$$

With Date of End of Efficacy Emergent Period defined in Section 7.11.6

The ESA-weeks are defined as the duration of ESA exposure. Each period when ESA [ATC code = B03XA] was taken will be summed by subjects as follows:

sum (each period (min(Analysis Date of last dose, End date of ESA therapy) + X days – Start date of ESA therapy +1)/7);

X will be defined as the duration of the effect of ESA following the last ESA administration for each ESA therapy use period, based on the following rules:

If Frequency = 1 PER WEEK then X=7

If Frequency = 2 PER WEEK then X=3

If Frequency = 3 PER WEEK then X=2

If Frequency = 1 PER MONTH then X=28

- If Frequency = ONCE then X=0
- If Frequency = BIM (Bi-monthly) then X=14
- If Frequency = QD (daily) then X=1
- If Frequency = QM (monthly) then X=28
- If Frequency = QOD (every other day) then X=2
- If Frequency = TID (three times daily) then X=1
- If Frequency = 4 TIMES PER WEEK then X=2
- If Frequency = EVERY 3 WEEKS then X=21

Additional frequency may be considered depending on the data.

6.1.3.8 Occurrence of iron supplementation.

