7.4.3.5 Categorical analysis for Hb values

For the analyses below, results will be displayed by treatment arm and type of ESA treatment.

Proportion of Hb values:

The proportion of Hb values >=10 g/dL and within 10-12 g/dL is a quantitative variable in the 0 – 100 range for each subject. Descriptive statistics for this variable will be presented. This variable will be presented in weeks 28-36, in weeks 44-52 and in weeks 96 -104, on the FAS.

Percentage of time during the Efficacy Emergent Period:

Descriptive statistics for the percentage of time with Hb values falling in each interval (<10.0 g/dL, >=10 g/dL, within 10.0-12.0 g/dL, > 12.0 g/dL, > 13.0 g/dL and > 14.0 g/dL) between the first and last Hb assessment during the Efficacy Emergent Period will be presented.

The number and percentage of subjects, and the number of events, will be reported by for the following potential EH events of interest, based on Hb values from the central laboratory:

- Hb increase by >2.0 g/dL between any two visits within 4 weeks of treatment

Time to first occurrence of potential EH will also be analyzed similarly as in Section [7.4.2.7](#) (except that all data during the Efficacy Emergent Period will be taken into account for the analysis).

Subjects with at least one Hb value > 13 g/dL during the treatment period will be summarized.

7.4.3.6 Occurrence (number) of hospitalizations, number of days of hospitalization per year and time to first hospitalization during the study.

The number and percentage of subjects with hospitalization will be reported. Descriptive statistics and frequency tabulations by treatment arm and type of ESA treatment of the total duration of hospitalization (days), the average duration of each hospitalization (days), the number of hospitalizations, number of days of hospitalization per year and reason for hospitalization will also be reported.

Time to first hospitalization will also be analyzed similarly as in Section [7.4.2.7](#) (except that all data during the Efficacy Emergent Period will be taken into account for the analysis).

Superiority will be declared if the upper bound of the two-sided 95% confidence interval of the hazard ratio of the two treatment arms is below 1.

The analysis will be done on the FAS.

7.4.3.7 Occurrence and time to first use of rescue therapy, occurrence and time to first use of RBC transfusions, number of RBC packs per subject, volume of RBC transfused per subject.

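### For subjects who discontinue because they die, the Efficacy Emergent Period stops at the last Hb assessment, so an admission or transfusion that starts between that assessment and death is not counted

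*SAP*

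**What the plan says.** SAP 7.11.6 gives the general rule that "the end of Efficacy Emergent Period is defined as the treatment period up to the EOT Visit", followed by one departure: "Only exception for subjects who discontinued due to death, the last Hb assessment is taken as per convention the date of death is the EOT". So the date of death is recognised as the EOT visit by convention, and is then replaced by the last Hb assessment.

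SAP 6.1 gives this period wide reach: "This period will be used as reference period for the time to event analyses related to efficacy endpoints, unless specified otherwise". It bounds four groups of endpoints:

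- Hospitalization (SAP 6.1.3.6): "The occurrence and the number of non-HD hospitalizations per subject during the Efficacy Emergent Period will be calculated". Days per year are divided by the length of the period.
- Rescue therapy (SAP 6.1.3.7): "Only rescue medication that started during the study treatment and up to end of efficacy emergent period will be taken into account".
- RBC transfusion (SAP 6.1.3.7): volume, packs and time to first transfusion are all taken within the period.
- IV iron (SAP 6.1.2.3 and 6.1.3.8): use to week 36 stops at the earlier of the week 36 visit and the end of the period. Later use is bounded by the period itself.

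Subjects with no hospitalization, rescue or transfusion are censored at the end of the period. For time to first hospitalization (SAP 7.4.3.6) and again in the rescue section (SAP 7.4.3.7), the plan states, with 1 as the threshold: "Superiority will be declared if the upper bound of the two-sided 95% confidence interval of the hazard ratio of the two treatment arms is below".

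The Safety Emergent Period in SAP 7.11.5 is handled differently. The date of death is itself one of its possible end points.

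**The concern.** Stopping at the last Hb is reasonable for an endpoint made of Hb values, because nothing can be observed after the last one. It does not suit events recorded by date. A subject who has had a last Hb sample can still be admitted or transfused, and those dates are collected up to death.

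The cut applies only to subjects who die on treatment, and it removes the days just before death. Censoring there is informative: the subject leaves the risk set as event-free shortly before a period in which an event is plausible. Counts of admissions and transfusions would be too low, and hazard ratios that carry a superiority statement would rest on incomplete events.

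**Working it through.** The documents give no figure that depends on this rule, so there is nothing to reproduce. The check has two parts.

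**1. Tracing the definition.** SAP 7.11.6 sets the end date. SAP 6.1 and 6.1.3.6 refer to it, and SAP 6.1.2.3, 6.1.3.7 and 6.1.3.8 use it. No section restores events between the last Hb and death. The exception covers subjects who discontinued due to death. For a subject who stopped treatment earlier and died later, the period ends at the EOT visit in the ordinary way.

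**2. Size of the excluded interval.** Inputs from Protocol 2.2.1.3 and the Schedule of Assessments: visits weekly to week 8, every 2 weeks from week 10 to 36, then every 4 weeks; windows of ±2 days to week 36 and ±3 days after. Assumption: death is uniform between visits V days apart and Hb is drawn on schedule until death.

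- Mean gap from last Hb to death = V/2. Maximum = V, or V plus twice the window if windows are used in full.
- For an event starting L days before death, P(start falls after the last Hb) = max(0, 1 − L/V).
- If no study Hb is drawn after the event starts, this probability is 1.

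| Period | V (days) | Mean gap | Max gap | Max with windows | L = 3 | L = 7 | L = 14 |
|---|---|---|---|---|---|---|---|
| Weeks 1-8 | 7 | 3.5 | 7 | 7 + 4 = 11 | 1 − 3/7 = 0.57 | 0 | 0 |
| Weeks 10-36 | 14 | 7 | 14 | 14 + 4 = 18 | 1 − 3/14 = 0.79 | 1 − 7/14 = 0.50 | 0 |
| After week 36 | 28 | 14 | 28 | 28 + 6 = 34 | 1 − 3/28 = 0.89 | 1 − 7/28 = 0.75 | 1 − 14/28 = 0.50 |

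A missed visit lengthens the gap. With planned treatment of 52 to 104 weeks, the first 36 weeks make up 36/104 = 35% to 36/52 = 69% of planned time, so the last row does not describe the whole trial.

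**Illustration with assumed inputs.** The documents give no on-treatment mortality. Suppose 5% to 15% of 375 subjects per arm die on treatment and 30% to 60% of those have a terminal admission. That is 375 × 0.05 × 0.30 = 5.6 to 375 × 0.15 × 0.60 = 33.8 such admissions per arm. If each starts 7 days before death with Hb on schedule, the uncounted number is:

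- 0 if all deaths fall in weeks 1-8;
- 2.8 to 16.9 if all fall in weeks 10-36 (× 0.50);
- 4.2 to 25.3 if all fall after week 36 (× 0.75).

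**Effect by type of analysis.** Counts of admissions, packs and volume lose every event that starts in the gap. Time-to-first analyses change only where the lost event was the subject's first. In days of hospitalization per year, the denominator stops at the last Hb. SAP 6.1.3.6 measures each stay from admission to discharge and states no truncation, so a stay begun before the last Hb can contribute days that lie outside the denominator. IV iron to week 36 loses numerator and denominator together.

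**The case against.** The strongest reply is that the rule loses less than it first appears to, and in endpoints that carry little weight. Much of this stands.

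- **Rescue ESA.** Protocol 5.1.5 requires a low HemoCue Hb confirmed at two consecutive study visits before rescue ESA. Its start therefore follows a study-visit Hb, and a course begun on that visit day is inside the period. Loss is possible but less frequent.
- **Transfusion.** Protocol 5.1.5 also requires a HemoCue reading before and after transfusion. A schedule footnote requires both HemoCue and central laboratory Hb whenever Hb is assessed at an unscheduled visit. SAP 7.11.6 does not say which source defines the last Hb. Protocol 2.3 points to the central laboratory for all statistical analyses. If HemoCue counts, transfusions measured as required are recovered, but a terminal admission is not.
- **Status of the endpoints.** Hospitalization, rescue and transfusion are additional secondary endpoints outside the nine-test sequence of SAP 7.4.2. Only IV iron to week 36 is a key secondary.
- **Other reporting.** Inpatient hospitalization for an adverse event is a seriousness criterion, and serious TEAEs and deaths have their own rates and hazard ratios (SAP 7.5.1.4). The clinical information is not lost to the report, although this does not repair the efficacy endpoints.

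A reader might infer that nearly all terminal events are dropped. That would require no study Hb to be drawn once the subject is admitted, which the documents do not say. A reader might also infer that the superiority statements will favour the arm with worse survival. The documents give no deaths by arm and no basis for a change in hazard ratio, so that is a possibility only.

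**Conclusion.** The rule is wrong as written for event endpoints. In subjects who discontinue due to death, admissions and transfusions that start after the last Hb are excluded, and so, less often, are rescue ESA and IV iron. Those with no earlier event are censored as event-free just before the event.

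The size depends on trial period: the mean gap rises from 3.5 to 7 to 14 days, and the chance of missing an admission that starts 7 days before death rises from 0 to 0.50 to 0.75. These figures rest on uniform death times and on-schedule sampling; without sampling after admission the loss is complete. How much is lost for transfusions also depends on the unstated Hb source.

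The primary Hb endpoints and the power calculation do not depend on the rule, and the fixed sequence is essentially unaffected. The direction and size of any between-arm bias cannot be determined from the documents. The point is worth correcting because the truncation is informative, affects endpoints with stated superiority criteria, and is easily avoided.

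**What to change.** In SAP 7.11.6, for subjects who discontinued due to death, end the Efficacy Emergent Period at the date of death for the hospitalization, rescue therapy, RBC transfusion and IV iron endpoints. Apply the same date to events, denominators and censoring times, and end the days of any stay still open at death on that date. Keep the last Hb assessment as the end date for Hb-based endpoints only, and state whether it means central laboratory or HemoCue.

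The cost is a sentence or two in the SAP and one derived end-date variable. No new data are needed: Protocol 5.3.3.2 collects admission and discharge dates, Protocol 5.1.5 has rescue details recorded in the eCRF, and SAP 7.11.5 already uses the date of death. SAP section 1 allows revisions until database hard lock. After that, the same derivation can be reported as an additional analysis and justified in the study report.

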8 DOCUMENT REVISION HISTORY

Version	Date	Changes	Comment/rationale for change
1.0	04-Dec-2014	NA	Document finalized
2.0	22-Mar-2016	
 1) Reduction of the number of sensitivity analyses for the secondary endpoints. 2) Revise the ordering for the key secondary endpoints by moving up the QoL endpoints. 3) Implementation of the Time to event approach for the PPS and adjustment of the relevant sections. 4) Change from ITT to All Randomized as per Astellas standard. Definition remains unchanged. 5) Use of the Safety Emergent Period (i.e., last dose + 28 days) as evaluation period by default for the safety endpoints. 6) Use of the Efficacy Emergent Period (i.e last dose + 7 days) as evaluation period by default for most of the efficacy time to event endpoints. 7) Use of "Time to censoring" instead of "time at risk" for patient with no event for more clarity. 8) Clarification of time to censoring for events evaluated during the Safety Emergent Period/Efficacy Emergent Period. 9) Time to PCS vital signs added. 10) Time to PCS ECG focused to QTc instead of all ECG assessments. 11) Update regarding derivation of MAP values: average of the 3 measurements instead of 2 (now in line with FG SAP). 12) Implementation of the primary efficacy endpoint for the US 	
 1) To limit the additional analyses. 2) Due to the importance and relevance of the QoL endpoints 3) PPS definition has been revised in order to limit the exclusion of data by using a time to event approach rather than creating one PPS set for each period of interest. 4) Astellas standards requirement. 5) Clarify a consistent approach for all the safety endpoints by defining the evaluated period up to 28 days after last dose, which matched the AE analyses. 6) Clarify a consistent approach for time to event efficacy endpoints by extending the evaluated period up to 7 days after last dose. 7) Clarification of the wording. Time to censoring is more appropriate. 8) Based on the definitions of Efficacy/Safety Emergent period, time to censoring for all time to events have been updated accordingly. 9) Time to PCS were already planned for lab and ECG but not for Vital signs. This was added to maintain a consistent approach. 10) Time to event for PCS ECG other than QTc was considered not of interest. 11) Using the average of all 3 measurements is more efficient and is consistent with the other studies 12) This specific endpoint has

Version	Date	Changes	Comment/rationale for change
		
submission (change in Hb from baseline to the average level between week 28 and week 52) with the description of the statistical analyses including sensitivity analyses for missing data.
 
13) Interim analysis changed from week 36 to week 52.
 
14) Implementation of time to first hospitalization and time to first potential EH .
 
15) Update regarding the analysis on cholesterol data: use of all data as main analysis and fasted only as additional..
 
16) Reduction in the number of analyses of subgroup of interests.
 
17) Addition of the analysis of percentage of time when Hb > 12, 13 or 14.
 
18) MMRM model added for number of RBC and volume of RBC during the treatment period.
 
19) Removal of descriptive analysis on the categorical change form baseline in Total FACT-An Score.
 
20) Addition of an analysis on a subset of subjects with baseline PF subscore <40 and ≥40, and baseline VT subscore <50 and ≥ 50.
 
21) Updated rule for complete missing start date and end date for concomitant medications. In that case, the medication will be considered as both previous and concomitant instead of only concomitant.
 
22) For the analysis of monthly IV Iron use, MMRM has been replaced by ANCOVA.
 
23) Additional tables run on group of subjects enrolled after protocol
	
been added in protocol amendment 1.0.Sensitivity analyses for missing data were added following FDA feedback on the Fibrogen 064 study.
 
13) This has been changed in protocol amendment 1.0.
 
14) Due to harmonization with Fibrogen 064 study SAP and the expected difference in treatment durations
 
15) Due to the assumption that most samples were not taken fasted and harmonization with Fibrogen 064 study SAP.
 
16) To limit the total number of analyses and the volume of tables
 
17) The concept of percentage of time with high Hb values was implemented in order to account for differences in individual treatment durations.
 
18) Inferential analysis for RBC was missing in the v1.0.
 
19) Descriptive statistics for categorical change not necessary since analysis on absolute change already planned and considered sufficient.
 
20) Due to harmonization with Fibrogen 064 study SAP.
 
21) Previous rule considered too conservative since a missing year of start is usually for previous medications than concomitant. Decision was taken to consider such medications as both previous and concomitant.
 
22) MMRM model for monthly IV Iron was not adapted due the data distribution. Since monthly average will be calculated, ANCOVA is more appropriate.
 
23) Added in order to assess the


Version	Date	Changes	Comment/rationale for change
		amendment implementation 24) Addition of response endpoint up to week 52, regardless of rescue therapy in the additional secondary endpoint 25) Addition of a week 36 to 52 endpoints, in the additional secondary endpoints for Quality of Life. 26) Removal of ANCOVA with LOCF for the primary endpoint sensitivity analysis, and addition of ANCOVA with MI and PMM.	impact of substantial protocol amendment 1.0. 24) Corresponding with the endpoint for the US 25) Clinically relevant to have an endpoint to measure long term effect on quality of life. 26) Sensitivity analyses for missing data were added following FDA feedback on the Fibrogen 064 study.
3.0	10-Sep-2018	1) Updating the safety and efficacy periods 2) Additional Hb response definition as the average Hb \geq 10. 3) Add MMRM analyses regardless of rescue therapy using FAS for primary EU endpoint 4) Removed analysis using all Hb values using All Randomized. 5) Added time to first IV iron during day 1 to week 36 6) Added the analysis of Time to first VAT 7) Details were added in All Randomized section regarding exclusion of subjects from site [REDACTED] 8) Additional analyses on adverse event were added considering events occurring up to last dose +7 days 9) The unique identifiers of protocol deviations are updated 10) Removed other baseline factors except baseline Hb and randomization stratification factors in ANCOVA with MI	1) Adjusting for the different dosing frequencies, especially for darbepoetin. 2) To include Hb values above 12.0 (e.g. 12.3) also as a good response. 3) Harmonization of Phase 3 studies. 4) Duplicate analysis 5) Majority of subjects did not use IV iron; therefore, time to first use proposed as alternative to the actual dose of IV iron. 6) Included VAT AE specific safety analysis. 7) Site [REDACTED] was terminated due to GCP violations and it is now clearly mentioned in the population section that those subjects are excluded from all analysis set. 8) Due to harmonization with Fibrogen 064 study SAP. 9) Updated according to latest protocol deviations 10) Per team discussion, other baseline factors will not be included for ANCOVA with MI

